### 6.8.2. STATISTICS TO MEET SECONDARY AIMS

#### 6.8.2.1. TO DETERMINE THE KINETICS OF SARS-COV-2 ANTIBODIES AND CELLULAR IMMUNE RESPONSE IN EARLY, MID, AND LONG PERIODS OF IMMUNIZATION.

Two methods will be followed to study the kinetics of SARS-CoV-2 antibodies since symptoms onset. Locally Estimated Scatterplot Smoothing (LOESS) models will be fitted as a first descriptive approach. Then, nonlinear mixed-effects (NLME) models will be fitted to get the curves that would determine the kinetics.

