##### NONLINEAR MIXED-EFFECTS (NLME) MODELS

Mixed-effects models are generally useful when there are multiple measures per participant, as in this study. Random effects are included in the model to test if they may be causing any significant, and generally unexpected, significant influence in the modelling built by the fixed effects. Therefore, introducing random effects in the model help to control unobserved variance.

We will use NLME models to study possible differences in the dynamics (kinetics) of SARS-CoV-2 antibodies (IgM, IgG) levels since symptoms onset. After fitting a general model, the differences will be studied between clinical spectrums and biological sex, setting the largest group as reference groups for modelling. To fit these models, we will use all the data available except for those from participants who never tested positive. Time after diagnosis was discretized as follows: Tests made in the first 14 days since diagnosis are treated as "Day 15". Tests from days 15 to 29, as "Day 30", days 30 to 59 as "Day 60", days 60 to 89 as "Day 90", days 90 to 179 as "Day 180", days 180 to 269 as "Day 270", days 270 to 360 as "Day 360", and days 360 up to end of follow-up as "Day 450". However, antibody values beyond 450 days after diagnosis were not considered, as they were only available for 14 participants.

The general equations to be fitted will be:

$$IgM(t) = b_1 + (b_0 - b_1)e^{-k_1 t} - b_1 k_1 (e^{-k_1 t} - e^{-k_2 t})$$

$$IgG(t) = b_1 + (b_0 - b_1)e^{-k_1 t} - b_1 k_1 (e^{-k_1 t} - e^{-k_2 t})$$

Having  $t$  normalized per the maximum number of days (360). This general equation corresponds to an equation describing an exponential rise followed by an exponential decay.  $b_0$  corresponds to the baseline value,  $b_1$  corresponds to the asymptotic value (i.e., antibody levels at  $t \rightarrow \infty$ ),  $k_1$  corresponds to the rise rate, and  $k_2$  to the decay rate.

Nonlinear mixed-effects models will be built using the nlme package [14].

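### The NLME time coding places every test at or after the end of its interval, which distorts the absolute timing of the fitted antibody curve and leaves b0 extrapolated

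*Combined protocol and SAP*

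**What the plan says.** Section 6.8.2.1 plans two methods for antibody kinetics: a descriptive LOESS smooth, then NLME models whose curves are to describe the kinetics. It sets the clock at symptom onset: "Two methods will be followed to study the kinetics of SARS-CoV-2 antibodies since symptoms onset".

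The NLME subsection then gives a recoding rule on a different clock, beginning "Time after diagnosis was discretized as follows". The early rule is "Tests made in the first 14 days since diagnosis are treated as 'Day 15"; later ones are "days 90 to 179 as 'Day 180', days 180 to 269 as 'Day 270', days 270 to 360 as 'Day 360"; the last is "days 360 up to end of follow-up as 'Day 450". Values more than 450 days after diagnosis are left out.

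The model equations in t follow directly. Time is "normalized per the maximum number of days (360"), and b0 "corresponds to the baseline value". After a general fit, "the differences will be studied between clinical spectrums and biological sex".

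The LOESS subsection counts from the day of diagnosis and mentions no intervals. Section 6.6 defines a date of symptom onset, and section 12 lists it among the variables collected. Sections 6.5.1 and 6.6.2 count visits from the beginning of the study, not from diagnosis.

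**The concern.** The model is a continuous curve in time, so its timing is only as good as the times given to it. A rule that moves tests only to the right does more than coarsen the axis: it displaces the curve. The displacement is also uneven, since a test on day 89 becomes 90 while a test on day 90 becomes 180. A change of day zero therefore cannot absorb it.

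Secondary aim 1 asks about the early, mid and long periods of immunization. A curve displaced to the right can suggest that antibodies last longer than they do. Three loose ends sit in the same text: two time origins, day 360 in two intervals, and a stated maximum of 360 beside a top label of 450.

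**Working it through.** **1. The shift, from the documents alone.** For every whole day from 0 to 450, shift = label − actual day (here day 360 is labelled 360).

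| Days since diagnosis | Label | Smallest | Mean, even spread | Largest |
|---|---|---|---|---|
| 0–14 | 15 | 1 | 8 | 15 |
| 15–29 | 30 | 1 | 8 | 15 |
| 30–59 | 60 | 1 | 15.5 | 30 |
| 60–89 | 90 | 1 | 15.5 | 30 |
| 90–179 | 180 | 1 | 45.5 | 90 |
| 180–269 | 270 | 1 | 45.5 | 90 |
| 270–360 | 360 | 0 | 45 | 90 |
| 361–450 | 450 | 0 | 44.5 | 89 |

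Overall mean: (15×8 + 15×8 + 30×15.5 + 30×15.5 + 90×45.5 + 90×45.5 + 91×45 + 90×44.5) / 451 = 17,460 / 451 = 38.7 days. Labelling day 360 as 450 gives 38.9. No shift is negative.

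**2. Stretching.** The midpoints of the 60–89 and 90–179 intervals are 74.5 and 134.5. The 60 real days between them become 180 − 90 = 90 labelled days, which flattens the curve there.

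**3. b0.** The printed equation is y(t) = b1 + (b0 − b1)e^(−k1 t) − b1 k1 (e^(−k1 t) − e^(−k2 t)). At t = 0 it gives y = b0. The lowest labelled time is 15/360 = 0.042, so no observation lies at or near t = 0.

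**4. What this does to a fitted curve.** The documents give no parameter values and no test dates relative to diagnosis, so both are assumed. In each case the printed equation was taken as the truth and refitted on the labels.

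- *First set.* Three curves with simulated noise, fitted without random effects, under four test-timing patterns. The day of falling to half of peak was:

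| Test timing | IgG-like (true 304.5) | IgM-like (true 151) |
|---|---|---|
| Even spread | 351 | 194 |
| 0–7 days after nominal dates | 406 | 234 |
| Within 7 days either side | 373 | 198 |
| 1–7 days before nominal dates | 309 | 156 |

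 The delay therefore runs from about 5 days (309 − 304.5; 156 − 151) to about 100 (406 − 304.5). The third, slower curve gives no half-of-peak day over the range examined. With early tests the IgG-like peak came at day 71 against a true 72.5, so the peak can be almost unmoved. Fits on actual days recovered the truth.

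- *Second set.* Rise half-times of 3, 5, 10 and 15 days, decay half-lives of 60, 90, 120 and 180 days, seven visit patterns, no noise: 4 × 4 × 7 = 112 fits. Half of peak came later in all 112, by 8 to 75 days (median 44). The peak came later in 104. The fitted decay half-life rose in 86 fits and fell in 26. Fitted b0 (truth 0) was negative in 107 and positive in 5, and in 22 fast-rise fits it ran beyond −100 times the peak. For a 10-day rise and 90-day decay, the true peak at day 36 and half of peak at day 150 became days 46–60 and 160–213.

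**5. Time origin.** If time is meant to run from symptom onset, an assumed lag of 3 to 10 days from onset to diagnosis offsets some or all of the 8-day shifts. It leaves about 35 to 42 days in the later intervals (45 − 10; 45 − 3).

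**6. The scaling constant.** Let S be the constant and r the rise half-time in days. Then k1 = S ln2 / r. The second term has amplitude b1 k1, so S affects the shape as well as the units. For a 10-day rise and 90-day decay with b0 = 0, S = 360 gives k1 = 24.95 and asymptote/peak = 0.056. S = 450 gives k1 = 31.19 and 0.045, about 19% lower.

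**The case against.** The strongest reply is that the quantities shown to move are not the ones the plan names. It names b0, b1, k1, k2 and group differences, and plans no time to peak or to half of peak. This stands in part. The rates and b0 have no fixed direction of error, so a reader who infers that the decay half-life will be overestimated goes further than the evidence: it fell in 26 of 112 fits. The curve itself is still the planned product, and its position in time is displaced.

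Second, the size is conditional. This stands in full. All the assumed curves have low plateaus (asymptote/peak 1.3% to 11.5% in the 112-fit set). If the plateau exceeded half of the peak, a half-of-peak day would not exist. Tests made just before the nominal dates lose only about 5 days.

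Third, the labels might not be t, since a maximum of 360 does not fit a top label of 450. The mismatch is real, but the subsection gives the labels no other use. If they are for display only, the text should say so.

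Fourth, a reader might infer that the comparisons by clinical spectrum and sex are biased. The documents do not support that. Groups with the same kinetics and visit timing receive the same labelled curve, and visit timing by group is not given.

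Fifth, a reader might say that LOESS and NLME will contradict each other. The LOESS text is silent on intervals, so the most one can say is that they could.

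**Conclusion.** The point holds as a matter of absolute timing for secondary aim 1. The one-sided shift (mean 8 to 45.5 days by interval, about 39 overall, maximum 90) and the extrapolated b0 follow from the text, given that the labels are t; the means also assume evenly spread tests. The usual consequence is a decline that appears too late. Its size, about 5 to 100 days in the refits, rests on assumed kinetics and test dates and should not be read as an estimate. The primary aim is unaffected. It should be fixed, because the bias favours apparent persistence and the remedy is nearly free.

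**What to change.** Fit the NLME models on actual continuous days from one stated origin, and use that origin for LOESS. The actual day must be known to assign an interval, so the data are already held. Interval midpoints are a weaker repair: for the IgG-like curve they gave day 308 with evenly spread tests but 261 to 346 with clustered ones (true 304.5).

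Reconcile symptom onset (opening of 6.8.2.1 and the NLME text) with diagnosis (the recoding rule and LOESS). Diagnosis covers asymptomatic participants; onset can serve as a sensitivity fit where dates exist.

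Keep the intervals for tables only, and put day 360 in one of them.

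Do not change 360 to 450 as a tidy-up, because that alters the shape the equation can take. State one fixed scaling constant and keep it, or give the second exponential term its own amplitude parameter.

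The cost is revised SAP wording and a refit. The nlme package accepts continuous time, and no new data are needed.

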#### 6.5.1. RECRUITMENT

The Basic Prevention Unit of Northern Metropolitan Area of Barcelona (Primary Health Care and Hospital), Spain (NM\_BCN) offers HCW to participate in ProHEPIC-19 study, if they accept; the researchers of ProHEPiC-19 contact these participants.

Eligible participants interested in the study, are accurately informed about the ProHEPiC-19 protocol, and signed informed consent to participate.

Participants complete several clinical questionnaires and immune clinical determination at baseline, 7 days, 15 days, 3, 6, 9 and 12, 16, 20, 24 months after the beginning of the study. (see Table 2)

Participant data files will be stored in numerical order (code system) and in a secure and accessible place and manner. Participant files will be maintained in storage for a period of 15 years after completion of the study.

Anonymised demographic data will be collected for those participants who decline to take part in the project, to assess the external validity of the recruited sample of participants.

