A) RT-PCR will be used as diagnostic test every 2 weeks RNA for RT-PCR tests will be extracted from fresh samples using the STARMag 2019-nCoV kit (Seegene, CA, USA) on a liquid-dispensing robot (STARlet Hamilton, USA). To inactivate the virus and extract viral RNA, 500 µl of the transfer medium containing the swab is combined with 500 µl of lysis buffer of the STARMag kit in a BSL-2 laboratory; following 10' of incubation at room temperature, 350 µl was used for nucleic acid extraction into a volume of 100 µl of extracted genome, from which 8 µl was taken for the 2019-nCoV PCR assay. The detection of RNA will be performed using the Allplex™ SARS-CoV-2 Assay is a multiplex real-time PCR

assay to detect 4 target genes of SARS-CoV-2 in a single tube. The assay is designed to detect RdRP, S and N genes specific for SARS-CoV-2, and E gene for all of Sarbecovirus including SARS-CoV-2 (Seegene, CA, USA) according to the manufacturer's instructions.

B) Quantification of antibodies to SARS-CoV-2. We performed a previous validations study with 6 different IVD-CE approved ELISA tests and selected the commercially available test kits - the AntiSARS-CoV-2 IgG and IgM ELISA (Inmunodiagnostic). This ELISA test had a Sensitivity 92.5% and a specificity 93.3% for IGM and IgG against Nucleocapsid (N) and Spike (S) antigens. For this, the best reagents and the most relevant antigen specificities will be analysed. We will perform test at baseline, 7 days, 15 days, 3, 6, 9 and 12,16,20,24 months after the beginning of the study.

We conducted a pre-validation study (March-April 2020) with 6 different IVD-CE approved ELISA tests and selected commercially available Anti-SARS-CoV-2 IgG and IgM ELISA kits (Inmunodiagnostic Limited ©). These ELISA tests had a sensitivity of 92.5% and a specificity of 93.3% for IGM and IgG against the nucleocapsid (N) antigen. Positivity thresholds were provided by the assay manufacturers and were considered positive with an index value greater than 1.1, indeterminate from 0.9 to 1.1 and negative if <0.9 index units.

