**Secondary Outcome Measures:**

4. Kinetics of SARS-CoV-2. IgM Nucleocapside

IgM (nucleocapside) ELISA kits (Inmunodiagnostic Limited ©). Positivity thresholds were provided by the assay manufacturers and were considered positive with an index value greater than 1.1, indeterminate from 0.9 to 1.1 and negative if <0.9 index units

[Time Frame: Baseline, 7 days, 15 days, 3, 6, 9 and 12 months after the beginning of the study]

5. Kinetics of SARS-CoV-2. IgG Nucleocapside

IgG (nucleocapside) ELISA kits (Inmunodiagnostic Limited ©). Positivity thresholds were provided by the assay manufacturers and were considered positive with an index value greater than 1.1, indeterminate from 0.9 to 1.1 and negative if <0.9 index units

[Time Frame: Baseline, 7 days, 15 days, 3, 6, 9 and 12 months after the beginning of the study]

6. Kinetics of SARS-CoV-2. IgG Spike

IgG (spike). ELISA kits DECOV1901 (Demeditec Diagnostics GmbH©). Positivity thresholds were provided by the assay manufacturers and were considered positive with an index value greater than 40, indeterminate from 32 to 40 and negative if <32 UI/ml

[Time Frame: Baseline, 7 days, 15 days, 3, 6, 9 and 12 months after the beginning of the study]

7. Kinetics of SARS-CoV-2. T-Cell

SARS-CoV-2 specific CD4+ and CD8+ T-cell responses we performed an IFN $\gamma$  ELISPOT assay. Wells will be considered positive if they contained at least 50 spot-forming cells per 10^6 PBMCs above the background level (2X mean + 3Xstandard deviation).

[Time Frame: Baseline, 7 days, 15 days, 3, 6, 9 and 12 months after the beginning of the study]

8. To assess the relation between clinical variables and initial RT-PCR results in the whole sample and by sex.

To study the differences between clinical spectrums and initial RT-PCR we will use ANOVAs or Kruskal-Wallis tests, after checking normality assumption using a Shapiro-test

[Time Frame: Baseline, to 12 months after the beginning of the study]

9. To analyse the relation between clinical variables and the interindividual differences in the immune response in early, mid, and long periods of immunization in the whole sample and by sex

To study the differences between clinical spectrums and immune response in early period we will use ANOVAs or Kruskal-Wallis tests, after checking normality assumption using a Shapiro-test . Similarly, to look for differences in antibody levels between sex, either a t-test or a Mann-Whitney test will be performed.

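### The 450-day limit in the NLME antibody models rests on a count of 14 participants and removes all 16-, 20- and 24-month samples of anyone infected at or before entry

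*Combined protocol and SAP*

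**What the plan says.** The NLME subsection of 6.8.2.1 opens its data rule broadly: "we will use all the data available except for those from participants who never tested positive". It then groups time since diagnosis into bins. The last bin takes "days 360 up to end of follow-up as" Day 450. The next sentence adds the limit: "antibody values beyond 450 days after diagnosis were not considered, as they were only available for 14 participants". Below the equations, time is said to be scaled by a maximum of 360 days.

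The sampling schedule runs further. The laboratory part of section 6.6 says "We will perform test at baseline, 7 days, 15 days, 3, 6, 9 and 12,16,20,24 months after the beginning of the study", and section 6.5.1 gives the same visit months. The kinetics outcomes in section 6.6.2 stop earlier: "Time Frame: Baseline, 7 days, 15 days, 3, 6, 9 and 12 months after the beginning of the study". The abstract also describes a 12-month follow-up.

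**The concern.** The reason for the limit is a number of samples already counted, written in the past tense inside a plan that otherwise looks forward. Such a count grows as follow-up continues, but the exclusion it justifies is fixed. It is also not reconciled with the schedule, which deliberately collects blood after day 450.

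Long-term response is part of the stated purpose. Secondary aim 1 covers early, mid and long periods, and the primary aim names long-term immune response. In the model, b1 is defined as the antibody level as time goes to infinity. Leaving late values out of the main kinetics model therefore needs a reason based on the design or on biology, and the plan gives only availability.

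**Working it through.** **1. The count of 14.** This is an observed figure, so no formula reproduces it. Its timing can be checked. Section 6.3 gives a start of 31 March 2020 and an estimated end of recruitment on 15 June 2021.
- 31 March 2020 + 450 days = 24 June 2021, nine days after the estimated end of recruitment.
- Month 24 for a participant enrolled on 15 June 2021 is 15 June 2023.

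A count of 14 fits a data cut around mid-2021. The plan does not call it interim, so that is an inference.

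**2. Which scheduled samples fall past day 450.** Assumption: the schedule's starting point, the beginning of the study, means each participant's own entry. With 30.44 (or 30) days per month:

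| Visit | Days after entry | Kept only if diagnosis is at least this long after entry |
|---|---|---|
| Month 16 | 487 (480) | 487 − 450 = 37 days (30) |
| Month 20 | 609 (600) | 609 − 450 = 159 days (150) |
| Month 24 | 730 (720) | 730 − 450 = 280 days (270) |

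- Infected at or before entry: all three samples are excluded.
- Diagnosed at month 6 (day 183): the samples lie at 304, 426 and 548 days after diagnosis, so two of the three stay.
- Diagnosed at month 10: they lie at about 183, 304 and 426 days, so all three stay.
- Diagnosed more than about 85 to 90 days before entry (450 − 365 = 85; 450 − 360 = 90): the month-12 sample is excluded too. The non-recent infected group in section 6.5 has no upper limit on time since diagnosis, so this can occur.

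**3. Consistency within the subsection.** Four horizons appear: all available data, a last bin to the end of follow-up, a cut at day 450, and a maximum of 360 days. With a bin labelled Day 450, scaled time reaches 450/360 = 1.25. The scaling itself excludes nothing, but it shows that the horizon was not settled. LOESS has no 450-day limit, so the descriptive and the modelled curves can cover different ranges.

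**4. Precision lost.** The plan's equation is b1 + (b0 − b1)e^(−k1·t) − b1·k1·(e^(−k1·t) − e^(−k2·t)). The standard errors are the square roots of the diagonal of inv(J′J), where J holds the derivatives with respect to b0, b1, k1 and k2.

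The assumptions, none of them from the documents, are:
- a rise half-life of 7 days, k1 = 360·ln2/7 = 35.6;
- a decay half-life of 60 to 150 days, k2 = 360·ln2/half-life;
- equal residual variance and no random effects;
- sampling at days 3, 10, 18, 94, 185, 276 and 368, with or without day 33, compared with the same days plus 490, 612 and 733.

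Day 33 stands for the 1-month visit, which the abstract lists and section 6.5.1 does not.

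Ratio of standard errors, late samples dropped versus kept:

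| Decay half-life | b1, no 1-month sample | b1, with 1-month sample | k2, no 1-month sample | k2, with 1-month sample |
|---|---|---|---|---|
| 60 d | 1.36 | 1.12 | 1.30 | 1.08 |
| 90 d | 1.06 | 1.03 | 1.04 | 1.01 |
| 120 d | 1.02 | 1.01 | 1.04 | 1.04 |
| 150 d | 1.04 | 1.02 | 1.13 | 1.11 |

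The ratios barely change with b0 and b1. Between-person variation in b1 makes the loss for b1 smaller still.

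**The case against.** Several stronger readings are tempting, and the documents do not support them.

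- *Every late sample is discarded.* The limit counts from diagnosis and the schedule from the beginning of the study. The models include everyone who ever tested positive, so healthy-cohort members who convert later keep some or all late samples. The limit is stated for NLME only, and the samples remain available to LOESS and the bivariate tests.
- *Three of ten scheduled antibody tests are lost.* Sections 6.5.1 and 6.6 list ten time points, but Table 2 makes Visit 2 a telephone call for recently infected workers, ends at Visit 9 and gives no months. The fraction cannot be established.
- *Only the late samples identify the asymptote.* In the plan's equation b1 also multiplies the rise-and-fall term, so early and peak values carry much of the information on it. Much larger losses arise only if the peak height gets its own parameter, and the plan does not specify that model.

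Two arguments for the limit have weight. First, the kinetics outcomes end at 12 months, and 450 days covers that window for anyone diagnosed up to about 85 days before entry. But the plan keeps values beyond 12 months and does not give the outcome window as its reason. The 12- versus 24-month conflict still has to be settled. Second, late values have had more time to be affected by vaccination or reinfection, and a curve with one rise and one decay cannot represent a boost. Simply deleting the limit could therefore bias b1. That argument stands, and the fix has to deal with it.

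**Conclusion.** The concern holds in limited form. The 450-day limit is set by a count that is very likely a snapshot, and it is not reconciled with the 16-, 20- and 24-month sampling or with the other horizons in its own subsection. As written, it removes from the NLME models all three late samples of participants infected at or before entry.

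The statistical cost is usually small. The standard error of b1 grows by about 1 to 6% at decay half-lives of 90 to 150 days. At 60 days it grows by about 12% with a 1-month sample and 36% without. These figures depend on assumed half-lives and a simplified calculation. The stronger argument is that a data-dependent exclusion should not define the time range of the main kinetics model, especially when long-term response is an aim.

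**What to change.** 1. Remove the exclusion based on 14 participants. Fit the NLME models to all available values on actual days since diagnosis instead of bin labels. Alternatively, state a horizon derived from the design.
2. In either case, reconcile the follow-up length across the abstract, sections 6.5.1, 6.6 and 6.6.2, and the time scaling in 6.8.2.1.
3. State in advance how values after vaccination or reinfection are handled, using the recorded dates either to censor later values or to model them.
4. Report the fit with and without values after day 450, with the number of participants contributing to each.

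The cost is mainly SAP text, with no new sampling. Late estimates will rest on fewer participants and have wider intervals. Handling vaccination and reinfection adds some analysis work.

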## 5. HYPOTHESES AND OBJECTIVES

### 5.1 HYPOTHESES

The specific hypotheses are:

Infection with SARS-CoV-2 will produce different levels of immune response with respect to:

1. The kinetics and immune response is different depending on the clinical spectrum of COVID-19 disease.
2. The immune response is conditioned by age, sex and other clinical variables
3. Cytokines are good biomarkers to identify COVID-19 disease progression.

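### The antibody-kinetics equation ties the decaying term's height to b1 × k1, so its fitted rise rate, decay rate and asymptote describe the true kinetics only if that constraint happens to hold

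*Combined protocol and SAP*

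**What the plan says.** Section 6.8.2.1 gives the NLME models the main role in secondary aim 1: "nonlinear mixed-effects (NLME) models will be fitted to get the curves that would determine the kinetics". Under the NLME heading, the same equation is printed for IgM and for IgG: "IgM(t) = b_1 + (b_0 - b_1)e^{-k_1 t} - b_1 k_1 (e^{-k_1 t} - e^{-k_2 t", then closing brackets.

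The text describes its shape as follows: "This general equation corresponds to an equation describing an exponential rise followed by an exponential decay". It defines b0 as the baseline, b1 as the limit at long times, k1 as the rise rate and k2 as the decay rate. Time is "normalized per the maximum number of days (360"), although the last time category is Day 450. Time is also grouped. The sentence beginning "Tests made in the first 14 days since diagnosis are treated as" assigns those tests to Day 15, and the later categories are Days 30, 60, 90, 180, 270, 360 and 450.

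After a general fit, "the differences will be studied between clinical spectrums and biological sex". This serves the first hypothesis in section 5.1: "The kinetics and immune response is different depending on the clinical spectrum of COVID-19 disease".

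The documents give no derivation of the b1 × k1 factor, no check of it and no alternative form.

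**The concern.** A curve that rises and then decays to a plateau needs five quantities: a starting level, a plateau, two rates, and the height of the decaying part above the plateau. The printed equation has four. The missing one, the height, is set to b1 × k1.

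The ratio of peak component to plateau is then dictated by the rise rate and by an arbitrary time divisor, not by the data. When the data disagree, least squares or likelihood fitting can only respond by shifting b1, k1 or k2.

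This matters most for the group comparisons. Section 4 reports that the highest antibody responses have been seen in more severe disease, so groups are likely to differ in peak height. The equation turns that difference into apparent differences in waning and long-term level, which are the quantities hypothesis 1 is about.

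**Working it through.** **Algebra (no data needed).** Collecting terms in the printed equation:

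y(t) = b1 + (b0 − b1 − b1·k1)·e^(−k1·t) + b1·k1·e^(−k2·t)

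- y(0) = b0 and y(∞) = b1, so within the model the labels for b0 and b1 are correct.
- The coefficient of the decaying exponential is b1·k1, so amplitude ÷ asymptote = k1.
- With t = days/360, k1 = 360 × ln 2 ÷ (rise half-time in days). For 7 days this is 249.5 ÷ 7 = 35.6; for 14 days, 17.8; for 30 days, 8.3.
- With 450 as the divisor, the 7-day value becomes 311.9 ÷ 7 = 44.6. The constraint changes with the time unit.
- At exactly b1 = 0 the curve is b0·e^(−k1·t). It cannot rise, and k2 drops out.

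**Effect on a group comparison.** The documents give no antibody data, so every true value here is an assumption: b0 = 0.3, asymptote 1.0, rise half-time 7 days and decay half-life 90 days in both groups, with amplitude 3 in one and 12 in the other. Data were generated without noise from y = b1 + (b0 − b1)e^(−k1·t) + A(e^(−k2·t) − e^(−k1·t)). The printed equation was fitted by least squares from many starting values.

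| Setting | Decay half-life, A = 3 vs 12 (truth 90 d) | Asymptote (truth 1.0) |
|---|---|---|
| Plan's eight bins | 49 vs 112 d | 1.14 vs 0.29 |
| Plan's bins, b0 fixed at 0.3 | 217 vs 112 d | 0.07 vs 0.30 |
| Days 0 and 7 added | 213 vs 111 d | 0.07 vs 0.31 |

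- Fitted rise half-times in the first row are 32 vs 6 days.
- With noise (assumed SD 0.1 per bin mean, 300 runs), the first-row medians are 49 vs 112 days and 1.13 vs 0.29.
- With a true asymptote of 0.2, the decay half-lives are 104 vs 87 days, a smaller distortion.
- The fit has competing solutions on the plan's bins. For A = 3: SSE 0.044 (49 d) and SSE 0.130 (about 223 d, with b0 driven far below zero). For A = 12: SSE 0.221 (112 d) and SSE 0.334 (76 d, asymptote 1.09).
- When the true A equals b1·k1, recovery is exact.

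**Second set of assumed truths** (b0 = 0.2, b1 = 1, day 0 plus the plan's bins, five values of A/(b1·k1) for each of two pairs of half-lives):

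| True rise / decay half-life | A/(b1·k1) | Fitted b1 | Fitted rise | Fitted decay |
|---|---|---|---|---|
| 14 / 90 d | 1 | 1.00 | 14.0 d | 90 d |
| 14 / 90 d | 0.5 | 0.43 | 12.7 d | 118 d |
| 14 / 90 d | 0.25 | 0.19 | 11.3 d | 176 d |
| 14 / 90 d | 0.1 | 1.13 | 26.2 d | 35.2 d |
| 30 / 120 d | 0.5 | 1.20 | 39.2 d | 78.5 d |
| 30 / 120 d | 0.1 | 1.06 | 44.7 d | 55.4 d |

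The printed form recovered the truth in 2 of the 10 scenarios, those with ratio 1. A free amplitude recovered all 10. In the last row the root mean square error is only 0.009 although the decay half-life is less than half its true value, so a close fit does not show that the parameters are right.

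The time unit also matters. For 14/90 days and A = 4, dividing by 360 gives b1 = 0.17 and 189 days, whereas dividing by 30 gives 1.19 and 104 days.

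**The case against.** - **The labels are correct inside the model.** This is true: b1 is the model's limit, and k1 and k2 are its rate constants. The fault is a hidden constraint, so the fitted values need not estimate the real rise, decay and plateau.
- **The 49 vs 112 day contrast also reflects the missing early data.** This stands. On the plan's bins the amplitude-3 fit puts b0 near 2.5 against a true 0.3. With b0 fixed or early days added, the bias for that group changes sign. Bias is shown, but its direction is not established.
- **The calculations are not the planned analysis.** They fit one curve per group through eight points, whereas the plan fits participant-level mixed models, and they place the true values exactly at the bin days. Random effects add variation between participants but do not give the decaying term a mean amplitude of its own.
- **A factor may have been lost in typesetting.** This cannot be excluded. A lost divisor such as (k1 − k2) would make the forced ratio for 7 and 90 days about 1.1 instead of 35.6 and would remove the dependence on the time unit. The magnitudes would change. Amplitude would still be tied to the other parameters, and the text would still need correcting.
- **Reach is limited.** The primary outcome is unaffected. The LOESS curves and bivariate tests do not use this equation and could reveal a poor fit. For amplitude 3 the fitted curve stays within 0.14 of the truth at every bin. But those analyses do not estimate the kinetic parameters, and a close fit does not protect them.

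**Conclusion.** The concern holds. The algebra is exact for the equation as printed: amplitude is fixed at b1·k1, the ratio to the asymptote depends on the time divisor, and nothing in the documents justifies or tests this. Unless the true amplitude happens to match, fitted k1, k2 and b1 do not estimate the true kinetics, and differences in peak height pass into the rate and plateau comparisons.

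The size rests on assumed truths. In the second set of scenarios the decay half-life was off by about −61% to +96% and the asymptote by −81% to +20%. In the two-group example, identical decay half-lives came out about twofold apart (49 vs 112 d, or 217 vs 112 d), in opposite directions depending on how b0 and early time points were handled.

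This should be fixed before the models are used for secondary aim 1 and hypothesis 1. It does not touch the primary aim.

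**What to change.** Replace b1·k1 by a free amplitude A for each antibody:

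y(t) = b1 + (b0 − b1)e^(−k1·t) + A(e^(−k2·t) − e^(−k1·t)), with k1 > k2 > 0

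Let A differ by clinical spectrum and sex. The printed form is the special case A = b1·k1, so the constraint can be tested. If the printed expression is a typesetting slip, the same replacement applies. Fit on the actual days since diagnosis from which the bins are built, or keep the bins and fix b0. State the starting values and report several.

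**Cost.** One equation, one more fixed effect per antibody, more convergence work, and either unbinned time or a fixed b0. The secondary outcomes schedule antibody tests at "Baseline, 7 days, 15 days, 3, 6, 9 and 12 months after the beginning of the study", so early samples are planned, but the binning moves every test from the first 14 days to Day 15. That leaves b0 and k1 weakly identified. At an assumed SD of 0.1 per bin mean (A = 6, b1 = 1), the standard errors are:

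- b0: 3.1 against a true 0.3
- rise half-time: 2.6 days against 7
- decay half-life: 10.6 days against 90
- b1: 0.14 against 1.0

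The last two remain usable. Fixing b0 cuts the standard error of the rise half-time to 0.6 days. Adding days 0 and 7 cuts it to 0.46 days, and that of b0 to 0.10. Fixing b0 wrongly at 0 or 0.9 still returns a decay half-life of 87 to 91 days and an asymptote of 0.99 to 1.01.

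With b0 estimated on the bins and A = 3, the 10th to 90th percentile of the rise half-time is 2.4 to 17.5 days. The plan should therefore say that k1 will not be interpreted if it remains this poorly estimated.
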